9.2 Acceptability

For the secondary endpoint of acceptability, all mothers with non-missing responses for the questions (#1 or #2, #5, #6 and #7) on the Behavioral Assessment – Month 3 Follow Up eCRF will be included in the analysis. Mothers with some missing responses to the identified questions will be included in each part of the acceptability analysis as appropriate. The questions are outlined below where <study product> is their randomized assignment:

- Question #1 states "Overall, how much do you like using the pill?" with options 1. Dislike very much, 2. Dislike, 3. Neither like nor dislike, 4. Like, and 5. Like very much. (Reported only for participants assigned to the Truvada arm.)
- Question #2 states "Overall, how much do you like using the vaginal ring?" with options 1. Dislike very much, 2. Dislike, 3. Neither like nor dislike, 4. Like, and 5. Like very much. (Reported only for participants assigned to the DPV VR arm.)
- Question #5 states "Would you be willing to use <study product> for HIV prevention when breastfeeding in the future?" with options 1. Yes, 2. No, and 3. Not sure.
- Question #6 states "If the vaginal ring or oral PrEP were available to you, which product would you prefer to use for HIV prevention?" with options 1. Vaginal ring, 2. Oral PrEP, 3. Either – I find either product acceptable, and 4. Neither – I find neither product acceptable.
- Question #7 states "If the <study product> were available to you, would you prefer to use <study product> or male condoms for HIV prevention?" with options 1. <study product>, 2. Male condoms, 3. Either – I find either product acceptable, and 4. Neither – I find neither product acceptable.

Consistent with the secondary objective to characterize acceptability of study products in breastfeeding women, we will focus on three aspects of acceptability of the study products:

1. Overall attitude about assigned study product.
2. Willingness to use the assigned study product in the future.
3. Preference for:

- a. either study product and
- b. assigned study product compared to other HIV preventions methods (condoms).

For the first aspect, the participants' overall attitude about the assigned study product will be summarized by study arm. Question #1 ("Overall, how much do you like using the pill") is completed by participants assigned Truvada and Question #2 ("Overall, how much do you like using the vaginal ring") is completed by participants assigned to the VR. A bar chart and a table will be used to summarize the distribution of the responses to these 5-point Likert scale questions. The table will include the number and percentage in each response category and the mean, SD, median, IQR, and range. In addition, the participants who respond with 4 ("Like") or 5 ("Like very much") to Questions #1 and #2 will be considered as having a positive overall attitude about their assigned study product. The binomial proportions along with the corresponding 95% CI for each study arm will be used to assess overall attitude of their assigned study product. The study arms will be compared using the Fisher's exact test. Tables will be presented by arm and by site.

For the second aspect, the number and percentage of participants who would be willing to use their assigned study product in the future will be summarized by study arm. Participants who respond with 1 (yes) to Question #5 (Would you be willing to use <study product> for HIV prevention when breastfeeding in the future?) will be considered as willing to use the study product in the future. The binomial proportions along with the corresponding 95% CI for each study arm will be used to assess the willingness to use the study products in the future. The study arms will be compared using the Fisher's exact test.

For the third aspect part a, the number and percentage of participants who prefer the vaginal ring, oral PrEP, both or neither will be summarized by study arm. The proportions of participants along with the corresponding 95% CI for each option (ring, tablet, both or neither) of Question #6 (If the vaginal ring or oral PrEP were available to you, which product would you prefer to use for HIV prevention) will be used to assess study product preference by study arm. The study arms will be compared using the chi-squared test. For the third aspect part b, we use condom use as the other HIV prevention method. The number and percentage of participants who report the study product to be at least as acceptable as male condom use will be summarized by study arm. Participants who respond with 1 (study product) or 3 (Either – I find either product acceptable) to Question #7 (If the <study product> were available to you, would you prefer to use <study product> or male condoms for HIV prevention?) will be considered as finding the study product at least as acceptable for HIV prevention. The binomial proportions along with the corresponding 95% CI for each study arm will be used to assess the preference of HIV prevention methods. The study arms will be compared using the Fisher's exact test.

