10.5 Primary Endpoints

Maternal safety and Infant safety

To characterize the statistical properties of this study, Table 19 below presents the probability of observing zero, at least one, ten or more and fifty or more safety endpoints in each arm for various “true” event rates, ranging from low to high:

Table 19: Probability (%) of observing an event given different “true” event rates by cohort size

“True” event rate	P (0 events)		P ≥ 1 event		P (≥ 10 events)		P (≥ 50 events)	
	n=150	n=50	n=150	n=50	n=150	n=50	n=150	n=50
1%	22.15	60.50	77.85	39.50	8.94	0.00	0.00	0.00
5%	0.05	7.69	99.95	92.31	72.06	0.00	0.00	0.00
10%	0.00	0.52	100.00	99.48	96.62	0.94	0.00	0.00
15%	0.00	0.03	100.00	99.97	99.71	11.99	0.00	0.00
25%	0.00	0.00	100.00	100.00	99.99	73.78	0.85	0.00

^a Sample sizes in the table based on the proposed cohort sizes and study design. With 3:1 randomization, there will be 150 participants in the VR arm and 50 participants in the FTC-TDF arm.

An alternative way of describing the statistical properties of the study design is in terms of the 95% confidence interval for the “true” rate based on the observed data. Table 20 below shows the exact 2-sided 95% confidence intervals for the probability of an event based on a particular observed rate. For example, if none of the 150 participants receiving the VR regimen experience a safety event, the 95% exact 2-sided upper confidence bound for the true rate of such events in a particular arm of the study is 2.43%.

Table 20: Confidence intervals for endpoint rate (proportion of participants with endpoint) given number of endpoints (rows) in with number of participants (columns)

Number of events	Number of Participants	
	n=50	n=150
0	0.00, 7.11	0.00, 2.43
1	0.05, 10.65	0.02, 3.66
2	0.49, 13.71	0.16, 4.73
3	1.25, 16.55	0.41, 5.73
4	2.22, 19.23	0.73, 6.69
5	3.33, 21.81	1.09, 7.61
6	4.53, 24.31	1.48, 8.5
8	7.17, 29.11	2.33, 10.24
10	10.03, 33.72	3.24, 11.92
12	13.06, 38.17	4.2, 13.56
15	17.86, 44.61	5.71, 15.96
20	26.41, 54.82	8.34, 19.84
30	45.18, 73.59	13.92, 27.3

^a Sample sizes in the table based on the proposed cohort sizes and study design.

Maternal safety (composite)

- All SAEs including maternal deaths in both study arms

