2.3 Randomization

Participants were randomized in a 3:1 ratio (VR:tablet) to the two arms of the study stratified by study site. The randomization scheme was generated and maintained by the MTN SDMC.

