2.5 Sample Size and Power

The target sample size was 200 mother-infant pairs randomized 3:1 to vaginal ring vs oral Truvada. A total of 197 mother-infant pairs were enrolled. The sample size is based upon feasibility, anticipated low drug concentrations, and the likelihood of a favorable safety profile. The statistical properties of the study are described using the probability of observed safety events defined in the primary endpoint. The probabilities of observing a safety event for various “true” event rates were calculated. For example, if the true safety event rate was 5%, the probability of observing zero safety events is 0.05% for the cohort size of 150 participants (DPV VR) and is 7.69% for cohort size of 50 participants (Truvada). An alternative way of describing the statistical properties is in terms of 95% confidence interval. For example, if none of the participants experience a safety event, the 95% exact 2-sided upper confidence bound for the true event rate is 2.43% for participant receiving the VR regimen and is 7.11% for participants receiving Truvada. The properties above also inform the hypotheses around drug detection where number of events is the number of participants with detectable drug levels. Further details of the statistical properties for this study are described in section 10.5 of the protocol.

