5. GENERAL ANALYSIS METHODS

Descriptive statistics will be used to assess group characteristics or differences by study arm. Categorical variables will be summarized using the number and percent in each category. The Pearson-Clopper method¹ will be used to obtain a 95% confidence interval (CI) on the proportion of binary variables where applicable. Continuous variables will be summarized using the number of non-missing values, mean, median, standard deviation, quartiles and range (minimum, maximum) unless otherwise indicated.

The study arms will be identified and formatted as "DPV vaginal ring" and "Truvada oral tablet".

When use of formal testing to assess differences is required, the following methods will be used unless otherwise specified: Fisher's exact test or logistical linear regression for categorical response variable; t-test or linear regression for continuous outcomes. Hypothesis tests for the primary and secondary endpoints comparing the two study arms will have a two-sided significance level of 5%.

Within study arm assessment of the change from baseline measurement to a follow up measurement will be analyzed using McNemar's test (for categorical response variables) or the paired t-test or Wilcoxon signed-rank test (for continuous variables).

To assess the adequacy of the randomization, participants in each of the two arms will be compared for baseline characteristics including demographics and laboratory measurements using descriptive statistics. No formal statistical comparisons will be performed.

As mentioned previously, there may be more than the usual amount of missing data in this study. Appropriate methods will be used to characterize and adjust for missingness as described in Section 3.2 above.

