6. TRIAL PARTICIPANT DISPOSITION

6.1 Disposition of Participants

Enrollment of participants took place at four sites in Africa: Blantyre, Malawi; Zengeza Zimbabwe; Kampala, Uganda; Shandukani, South Africa (Johannesburg, SA). The mothers and infants screened and the reasons for those not enrolled will be summarized in tables by study site. The mother/infant pairs screened and enrolled by month will be summarized by study site. In addition, a consort diagram will describe the screening, eligibility, enrollment, randomization, and discontinuations from study participation. The consort diagram (or a separate table as appropriate) will describe the number of the participants with the minimum required data (from assays or eCRFs as described in Section 3.1 above) for inclusion in the primary and secondary analyses.

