9. SECONDARY ENDPOINT ANALYSES

9.1 Adherence

For the secondary endpoint of adherence, all mothers will be included. A secondary sensitivity analysis will be conducted including only mothers with drug concentration results for at least one visit after Enrollment.

For women randomized to the VR arm, a combination of measures will be used to characterize use of study product. In addition to the summary of maternal plasma DPV concentrations as described above in section 8.3, the residual DPV levels in the returned used rings will be summarized by study visit.

For women randomized to Truvada, maternal FTC-TP and TFV-DP concentrations from DBS sample collections, as described above in section 8.3, will be used to quantify study product use.

Cut-point Analyses

Drug levels will be summarized (number and percent) by categories defined by the following cut-points for each product. Because DPV ring release rates have not been verified against directly observed use, the only comparable category for the two products is no use.

DPV ring:

No use (rate \leq 0.9mg/month)
Some release (0.9mg/month $<$ rate \leq 4.0mg/month)
High release (rate $>$ 4.0mg/month)

Truvada:

No use (<16.6fmol/punch)
Some use (16.6-699fmol/punch)
High use (\geq 700fmol/punch)

DPV release rate is defined as the amount of DPV released from the ring divided by the duration of time during which the participant had the ring. The amount of DPV release is calculated by subtracting the

amount of residual DPV in a returned ring from the amount of DPV in control rings from the same lot number.

The number and proportion of participants visits with concentrations indicative of non-adherence (no use) will be compared by study arm using generalized estimating equations (GEE) with a Poisson link, an offset of number of tests for drug concentration, an exchangeable correlation structure and robust errors. The comparisons will be done using the cut-point levels described above for the two study arms: 1) residual ring data for participants assigned to the VR arm and 2) plasma data for participants assigned to Truvada. Trends over time in study product use will be explored using GEE.

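### The secondary arm comparisons leave out site, the randomisation stratum, and so lose some power if answers or product use differ between sites

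*SAP*

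**What the plan says.** SAP 2.3 states: "Participants were randomized in a 3:1 ratio (VR:tablet) to the two arms of the study stratified by study site". Protocol 10.7 agrees. SAP 6.1 adds: "Enrollment of participants took place at four sites in Africa", one in each of four countries.

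SAP 5 makes the arm comparisons formal tests: "Hypothesis tests for the primary and secondary endpoints comparing the two study arms will have a two-sided significance level of 5" per cent. The comparisons that are then specified are these:

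- **Acceptability, SAP 9.2.** For overall attitude (Questions 1/2), willingness (Question 5) and preference against condoms (Question 7): "The study arms will be compared using the Fisher's exact test". For preference between the products (Question 6): "The study arms will be compared using the chi-squared test".
- **Adherence, SAP 9.1.** Counts of visits classed as non-use "will be compared by study arm using generalized estimating equations (GEE) with a Poisson link, an offset of number of tests". The working correlation is exchangeable and the errors are robust. No covariate is named.

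In 9.2 site serves only to break down tables. SAP 5 allows regression as a general method but names no covariate, and 9.2 replaces it with specific tests. The primary safety and drug-detection endpoints are summarised per arm with exact intervals; SAP 8 specifies no arm test for them.

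**The concern.** Stratifying by site makes the arms nearly alike in site mix. If site predicts the outcome, the true sampling variation of the difference between arms is then smaller than an unstratified test assumes. The p-value comes out too large on average, and power is lost.

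The documents make site differences plausible without giving their size. Protocol 2.7.3 describes an earlier ring trial in the same four countries, with an analysis that set aside two sites with lower retention and adherence; the estimated risk reduction moved from 27% to 37%. Protocol 2.10.2 reports tablet adherence by drug level from under 30% to 86% across studies.

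The tablet arm has about 49 mothers. With an arm that small, a non-significant comparison could be read as showing that the two products are equally acceptable, so avoidable conservatism matters.

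**Working it through.** **1. The plan's own figures.** No power is stated for any arm comparison; SAP 2.5 gives per-arm precision. These figures reproduce: 0.95^150 = 0.05% and 0.95^50 = 7.69%. With no events, the exact upper bounds are 1 − 0.025^(1/150) = 2.43% and 1 − 0.025^(1/50) = 7.11%.

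**2. Inputs.** From SAP 2.5: "A total of 197 mother-infant pairs were enrolled". At 3:1 that is about 148 and 49 (planned 150 and 50, Protocol 10.5). The test level is two-sided 5%. Assumed, because not given: near-equal sites (ring 37 each; tablet 13, 12, 12, 12), all site-specific rates, and a log odds ratio of 1.0 as the difference to detect.

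**3. Type I error by formula.** Let f be the share of outcome variance due to site. With site-balanced arms, the pooled test's true level is about 2 × [1 − Φ(1.96/√(1 − f))]. Take favourable shares of 50, 75, 90 and 95%:

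- mean 0.775; variance between sites 0.030625; total variance 0.775 × 0.225 = 0.174375
- f = 0.030625/0.174375 = 0.176
- level = 2 × [1 − Φ(1.96/√0.824)] = 2 × [1 − Φ(2.159)] = 3.1%

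**4. Simulation for SAP 9.2.** I ran 200,000 trials per cell. The stratified test (CMH) is [Σ(x − E)]²/ΣV without continuity correction. For a site with n mothers (ring n₁, tablet n₂) and m favourable answers, x is the favourable ring count, E = n₁m/n and V = n₁n₂m(n − m)/[n²(n − 1)]. Entries are percentages for Fisher / chi-squared / CMH, with the thirteenth tablet mother in the lowest-rate site.

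| Favourable by site | Type I error | Power, ring lower | Power, tablet lower | CMH minus chi-squared, four settings | Same, exactly 36:12 per site |
|---|---|---|---|---|---|
| 85 everywhere | 3.8 / 4.7 / 4.8 | 64.7 / 68.9 / 68.3 | 69.1 / 73.9 / 74.0 | −0.6 to 0.1 | −0.5 to −0.1 |
| 80, 85, 85, 90 | 3.8 / 4.7 / 4.9 | 62.7 / 67.0 / 67.8 | 68.6 / 73.5 / 73.2 | −0.9 to 1.0 | −0.2 to 0.5 |
| 70, 80, 88, 95 | 3.2 / 4.2 / 4.8 | 57.4 / 62.4 / 67.7 | 66.6 / 71.3 / 72.2 | 0.9 to 5.3 | 2.0 to 4.0 |
| 50, 70, 85, 95 | 2.7 / 3.4 / 4.9 | 57.0 / 61.1 / 72.1 | 68.5 / 70.5 / 74.2 | 3.7 to 11.0 | 5.8 to 8.0 |
| 50, 75, 90, 95 | 2.4 / 3.1 / 4.9 | 49.0 / 54.7 / 68.2 | 64.0 / 66.4 / 70.9 | 4.5 to 13.5 | 7.2 to 9.6 |

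The four settings cross the direction of the difference with the site that holds the extra tablet mother (lowest or highest rate). Her placement matters. In the last row, under no difference, the pooled tablet share is (6.5 + 9 + 10.8 + 11.4)/49 = 76.9% against 77.5% for the ring, a small offset that helps or hurts a pooled test. Where it hurts, the gain from stratifying is about 4 to 6 points at 70–95% (6.5 with rates 70, 85, 90, 95) and about 9 to 13 at 50–95%. Where it helps, the gain is about 1 and about 4 to 7.

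**5. Fisher's own cost.** In these settings Fisher's power is 2.0 to 5.8 points below chi-squared, also when site has no effect. At 70% everywhere (ring lower) it is 0.3 (83.4 against 83.7). This comes from discreteness, not from leaving out site.

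**6. Adherence model, SAP 9.1.** Log-link Poisson with robust errors, three tests per woman, within-woman correlation 0.5 (assumed), rate ratio 0.55, 4,000 trials each, arm only → arm plus site:

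- no use 30% everywhere: type I error 5.4% → 5.5%; power 71.1% → 71.5%
- no use 15 to 45%: 4.2% → 5.6%; 68.7% → 72.6%
- no use 10 to 50%: 3.1% → 5.1%; 67.2% → 74.4%

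**The case against.** **Scope and direction.** Only secondary comparisons are affected. The stated aim there is to characterise adherence and acceptability, the sample size rests on feasibility, and the error is on the safe side. All of this stands. A reader might infer that all arm comparisons or the primary conclusions suffer, or that false positives are at risk; the documents support neither.

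**Size.** Large losses need site spreads of 45 points or so. This stands: at 80–90% the loss is negligible, and nothing in the documents fixes the spread.

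**The remedy.** With 12 or 13 tablet mothers per site, strata may be sparse. A conditional exact stratified test had power 78.1% against 79.5% for the planned Fisher test at site rates of 70–85%, and 75.8% against 77.0% at 65–90%. A continuity-corrected CMH gave 79.2% against Fisher's 83.4% at 70% everywhere. So the benefit depends on the variant chosen. This stands and shapes the fix.

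**Estimates.** It is tempting to add that omitting site pulls the odds ratio toward 1. The SAP plans no odds ratio for acceptability, and the Poisson rate ratio is collapsible, so a balanced omitted stratum does not attenuate it. That claim has no place here.

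**Text.** SAP 9.1 neither lists nor excludes covariates. A site term may be intended, but it is not stated.

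**Conclusion.** The point holds for the secondary endpoints. The specified acceptability tests ignore the randomisation stratum, and the adherence model does not state it. If site predicts the outcome, the tests are conservative: at site rates of 50–95% the true level falls to about 3% for chi-squared and about 2.5% for Fisher, while uncorrected CMH stays near 5%.

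The power lost against a pooled chi-squared test is about 0 to 1 point at 80–90%, up to about 6 at 70–95%, and up to about 13 at 50–95%. Chance imbalance within sites can bring the last two down to about 1 and 4. Fisher's discreteness is a separate cost, mostly 2 to 5 points. The whole gap between Fisher and a stratified test must therefore not be credited to site.

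These sizes rest on assumed site rates, near-equal sites and a log odds ratio of 1.0. The direction does not, provided site predicts the outcome.

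**What to change.** In SAP 9.2, replace the pooled tests of Questions 1/2, 5 and 7 with a site-stratified Cochran-Mantel-Haenszel test without continuity correction, and use its general-association form for Question 6. For the binary measures, report a site-stratified risk difference with 95% CI beside the per-arm proportions. In SAP 9.1, add site as a fixed factor in the GEE. If site is to stay out, say so and give the reason.

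Name the variant and the rule for sparse strata before the comparisons are run, for example the uncorrected test, or its mid-p version when counts are small. A plain exact or continuity-corrected version could do no better than the present Fisher test, or slightly worse. Sites where all mothers answer alike contribute no information to the stratified test.

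The cost is a few lines of SAP text; no new data are needed. With no site effect, uncorrected CMH stays within about 0.6 point of chi-squared in the settings above.

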10. SAFETY ANALYSES

See sections 8.1 and 8.2 for the description of the analyses of the primary safety endpoints. For the additional safety results below, no formal statistical testing will be performed.

10.1 Adverse Events

The following listings and tables of AEs will be presented separately for mothers and infants:

- A cumulative listing of AEs sorted by arm, site, and participant ID.
- Number and percentages of participants with AEs and number and percentages of AEs by body system/MedDRA preferred term and severity overall by arm, and by site.
- Number and percentages of participants with AEs and number and percentages of AEs by body system/MedDRA preferred term and relationship to study product overall by arm, and by site.
- An AE summary of the total number of participants with AEs and total number of AEs by severity and relationship to study product, overall, for each arm, and each site separately.

10.2 Product Holds

Instances of product hold for mothers as collected on the Product Hold Log eCRF will be described. The number and percentages of mothers who had a product hold at least once, the number of product holds, reasons for product holds, resolution of product hold, and duration of product hold (for those who were instructed to resume product use) will be presented in tables by arm and by site.

